8.3 End of Treatment (EOT) Procedures

Procedures to be performed during the EOT Visit are listed in the Appendix. Briefly, these include:

- Directed Physical Exam and ECOG performance status evaluation
- Vitals Signs, including weight
- Electrocardiogram (ECG) (Phase 1 Portion)
- Pregnancy Test – For Women of Childbearing Potential only (WCBP)
 - Either serum or urine pregnancy tests are sufficient
- Hematology:
 - white blood cell (WBC) count with differential, absolute neutrophil count (ANC), red blood cell (RBC) count, hemoglobin, hematocrit, platelet count
- Clinical chemistry and liver function:
 - sodium, chloride, potassium, glucose, blood urea nitrogen (BUN), creatinine, calcium, AST, ALT, total bilirubin, alkaline phosphatase, lactic acid dehydrogenase, total protein, albumin
- Creatine Kinase

- Thyroid panel:
 - Total T3, Free T4, and thyroid stimulating hormone
- Tumor imaging (if not done within 4 weeks of last study visit)
- Adverse event and concomitant medication collection and review
- Correlative studies blood collection

8.4 Short Term Follow-Up / 30 Day Safety Assessment

The 30 Day Safety Assessment Visit is a safety follow-up visit that is to be performed 30 days after the End of Treatment Visit Date (+/- 7) days). All efforts should be made to conduct this visit. If it is not possible to conduct the 30 Day Safety Assessment Visit, documentation of efforts to complete the visit should be provided.

The following procedures will be completed at the 30 Day Visit as designated in the Schedule of Assessments:

- Physical examination and ECOG performance status evaluation
- Vital signs, including weight
- Electrocardiogram (ECG) (Phase 1 Portion)
- Pregnancy Test – For Women of Childbearing Potential only (WCBP)
 - Either serum or urine pregnancy tests are sufficient
- Hematology:
 - white blood cell (WBC) count with differential, absolute neutrophil count (ANC), red blood cell (RBC) count, hemoglobin, hematocrit, platelet count
- Clinical chemistry and liver function:
 - sodium, chloride, potassium, glucose, blood urea nitrogen (BUN), creatinine, calcium, AST, ALT, total bilirubin, alkaline phosphatase, lactic acid dehydrogenase, total protein, albumin
- Creatine Kinase
- Thyroid panel:
 - Total T3, Free T4, and thyroid stimulating hormone
- Adverse Event and Concomitant Medication collection and review
- Survival status/post-study anticancer therapy status

8.5 Long Term Follow-Up / 90 Day Safety Assessment

AEs will be monitored and recorded in the subject's medical chart and research shadow chart from the time of first exposure to the investigational product avelumab, through 90 days (+/- 7 days) following last dose of a study drug. AEs with an onset date prior to the first exposure to an investigational product will not be followed, except in the case of clinically significant worsening of the AE during the specified AE monitoring time frame. Given the potential risk for delayed immune-related toxicities, safety follow-up must be performed up to 90 days after the last dose of avelumab administration. The extended safety follow-up beyond 30 days after last avelumab administration may be performed either via a site visit or via a telephone call with subsequent site visit requested in case any concerns noted during the telephone call.

8.6 Long-Term Follow-Up for Survival

Disease status and any subsequent anticancer therapy information status will continue to be monitored. Subjects will be followed for survival status via chart review or telephone contact every 12 weeks (+/- 2 weeks) from baseline for up to 2 years, or until disease recurrence, death, withdrawal of consent, or the study closes – whichever is earliest. Subjects will then be followed every 6 months (+/- 3 months) for survival status, until death or the study closes. Subjects who have a CR and discontinue therapy (section 4.1.4) should continue to return to clinic for assessment and scans every 12 weeks for two years. Extended follow-up will be performed as mentioned in **Section 9.7.1**

8.7 Imaging Assessments

Disease status will be assessed by CT or MRI scan of the chest, abdomen, and pelvis (CAP), in addition to any additional known disease sites (per institutional guidelines); image preparation and evaluation will follow the specifications provided in the RECIST version 1.1. The same modality (CT or MRI) must be used at screening and throughout the study. For subjects with stable disease or better per RECIST v1.1 criteria, scans will continue to be performed while receiving study treatment. Scans will follow this schedule even if a subject has a dosing delay that causes the beginning of a treatment cycle to be delayed.

CT/MRI scans to be performed at the following frequency:

- ≤28 days prior to C1D1
- Followed by every 12 weeks (± 1 week) from baseline, regardless of missed or delayed doses, until disease progression, withdrawal of consent, end of study, completion of protocol participation, or death – whichever occurs first.

An unscheduled scan for suspected disease recurrence/progression may be performed at any time at investigator discretion. RECIST reads via RECIST 1.1 should be performed on any imaging obtained for suspected disease recurrence/progression during the course of the trial.

8.8 .Analyte Listing

Table 1 - Analyte Listing

Chemistry	Hematology	Urinalysis	Other Labs
Sodium	WBC	Specific gravity	Pregnancy test
Potassium	RBC	pH	PT/INR
Bicarbonate	Hemoglobin	Blood	PTT
Chloride	Hematocrit	Protein	Amylase
Total protein	MCV	Glucose	Lipase
Albumin	MCH	Ketones	Creatinine Kinase (CK)
Calcium	MCHC	Microscopic	
Glucose	RDW		
BUN	Platelets		
Creatinine	Differential:		
Total bilirubin	-Neutrophils		
Alkaline phosphatase	-Lymphocytes		
AST (SGOT)	-Monocytes		
ALT (SGPT)	-Eosinophils		
Lactate	-Basophils		
Dehydrogenase			

8.9 Correlative Studies

8.9.1 Tumor Specimens

Subjects with paraffin embedded tumor available should have 10 slides collected for immunohistochemical staining with PD-1, PD-L1, and immune infiltrates. When possible, up to 2 additional curls, 1 mm thick should be obtained for nanostring analysis and TCR sequencing. This archival tissue does not need to be collected prior to initiating therapy on Week 1.

9.0 SAFETY

Monitoring for both acute and chronic toxicities will be evaluated at all study related visits and will be assessed by the Sponsor-Investigator. Toxicity information will be recorded and periodically reported to the the DSMB and EMD Serono. The Investigator will follow the guidelines below for treatment for toxicity. If a subject experiences toxicity, lab value abnormality, or other adverse event that is not described below, it will be up to the discretion of the treating Investigator if they want to delay study treatment and duration.

All adverse events and toxicity will be evaluated using NCI Common Terminology Criteria for Adverse Events (CTCAE) Version 5.0 as described in **Section 9.5**.

9.1 Adverse Event

According to ICH guidelines for Good Clinical Practice; 21 CFR 312.32, IND Safety Reports; and ICH E2A, Definitions and Standards for Expedited Reporting, an adverse event is defined as follows:

An adverse event is any untoward medical occurrence in a clinical investigation subject administered a medicinal product and which does not necessarily have a causal relationship with this treatment. An AE can therefore be any unfavorable and unintended sign (including an abnormal laboratory finding), symptom, or disease temporally associated with the use of a medicinal product, whether or not considered related to the medicinal product.

Abnormal laboratory values for laboratory parameters specified in the study should not be recorded as an adverse event unless an intervention is required (repeat testing to confirm the abnormality is not considered intervention), the laboratory abnormality results in a serious adverse event or the adverse event results in study termination or interruption/discontinuation of study treatment.

Medical conditions present at screening (i.e., before the study treatment is administered) should be captured as baseline in the subject's research shadow chart. Medical conditions present at baseline that worsen in intensity or frequency during the treatment or post-treatment periods should be reported and recorded as adverse events.

9.2 Serious Adverse Event

An adverse event should be classified as an SAE if it meets one of the following criteria:

Fatal	Adverse event results in death.
Life threatening:	The adverse events placed the subject at immediate risk of death. This classification did not apply to an adverse event that hypothetically might cause death if it were more severe.
Hospitalization:	It required or prolonged inpatient hospitalization. Hospitalizations for elective medical or surgical procedures or treatments planned before enrollment in the treatment plan or routine check-ups are not SAEs by this criterion. Admission to a palliative unit or hospice care facility is not considered to be a hospitalization.
Disabling/incapacitating	Resulted in a substantial and permanent disruption of the subject's ability to carry out normal life functions.
Congenital anomaly or birth	An adverse outcome in a child or fetus of a subject exposed to the molecule

defect:	or treatment plan regimen before conception or during pregnancy.
Medically significant:	The adverse event did not meet any of the above criteria, but could have jeopardized the subject and might have required medical or surgical intervention to prevent one of the outcomes listed above.

Classification of an event as serious or non-serious determines the reporting procedures to be followed.

9.3 Unexpected Adverse Event

An unexpected adverse event is defined as an event that has a nature or severity, or frequency that is not consistent with the applicable investigator brochure, or the prior medical condition of the subject or other treatment given to the subject. "Unexpected," as used in this definition, refers to an adverse drug experience that has not been previously observed and reported in preclinical or clinical studies rather than an experience that has not been anticipated based on the pharmacological properties of the study drug.

9.4 Monitoring and Recordings Adverse Events

All AEs will be assessed by the investigator or qualified designee and recorded in the subject's research shadow chart. The investigator should attempt to establish a diagnosis of the event on the basis of signs, symptoms and/or other clinical information. In such cases, the diagnosis should be documented as the adverse event and/or serious adverse event and not described as the individual signs or symptoms. The following information should be recorded:

- Description of the adverse event using concise medical terminology
- Description as to whether or not the adverse event is serious, noting all criteria that apply
- The start date (date of adverse event onset)
- The stop date (date of adverse event resolution)
- The severity (grade) of the adverse event
- A description of the potential relatedness of the adverse event to study drug, a study procedure, or other causality
- The action taken due to the adverse event
- The outcome of the adverse event

9.5 Grading Adverse Event Severity

All AEs will be graded in severity according to the NCI Common Terminology Criteria for Adverse Events (CTCAE) Version 5.0. If a CTCAE criterion does not exist, the investigator should use the grade or adjectives: Grade 1 (mild), Grade 2 (moderate), Grade 3 (severe), Grade 4 (life-threatening), or Grade 5 (fatal) to describe the maximum intensity of the adverse event.

9.6 Attribution of an Adverse Event

Association or relatedness to the study agent will be assessed by the investigator as follows:

- **Definite:** The event follows a reasonable temporal sequence from exposure to the investigational agent, has been previously described in association with the investigational agent, and cannot reasonably be attributed to other factors such as the subject's clinical state, other therapeutic interventions or concomitant medications; AND the event disappears or improves with withdrawal of the investigational agent and/or re-appears on re-exposure (e.g., in the event of an infusion reaction).
- **Probable:** The event follows a reasonable temporal sequence from exposure to the investigational agent and has been previously been described in association with the investigational agent OR cannot reasonably be attributed to other factors such as the subject's clinical state, other therapeutic interventions or concomitant medications.
- **Possible:** The event follows a reasonable temporal sequence from exposure to the investigational agent, but could be attributable to other factors such as the subject's clinical state, other therapeutic interventions or concomitant medications.
- **Unlikely:** Toxicity is doubtfully related to the investigational agent(s). The event may be attributable to other factors such as the subject's clinical state, other therapeutic interventions or concomitant medications.
- **Unrelated:** The event is clearly related to other factors such as the subject's clinical state, other therapeutic interventions or concomitant medications.

For general AE assessment, an AE is considered related if it is assessed as definitely or probably related; unrelated if it is assessed as possibly, unlikely related or unrelated.

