9.7 Adverse Event Recording Period

AEs will be monitored and recorded in the subject's medical chart and research shadow chart from the time of first exposure to the investigational product avelumab, through 90 days following last dose of a study drug. AEs with an onset date prior to the first exposure to an investigational product will not be followed, except in the case of clinically significant worsening of the AE during the specified AE monitoring time frame.

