9.8.3 FDA Reporting Requirements

The Sponsor-Investigator assumes responsibility for IND safety reporting to the FDA, in accordance with regulations under 21 CFR 312.32.

Each SAE report will be evaluated by the Sponsor-Investigator to assess the seriousness of the event, the expectedness of the event, and the relationship to participation in the study. For regulatory reporting purposes, the Sponsor-Investigator will determine expectedness relating to avelumab and trabectedin using safety information specified in the avelumab investigator brochure and trabectedin FDA-approved package insert. An event will be classified as related if the Sponsor-Investigator determines that the event may be related to the study drug.

For determination of IND safety reporting, AE attribution will be assessed according to the suspected adverse reaction definition described in 21 CFR 312.32 as an AE for which there is a reasonable possibility that the drug caused the adverse event

where “reasonable possibility” means there is evidence to suggest a causal relationship between the drug and the AE. Suspected adverse reactions that are serious, related, and unexpected will be reported to the FDA as an IND safety report, in accordance with regulations under 21 CFR 312.32.

The Sponsor-Investigator will provide written notification of safety report to the FHCRC IRB per IRB policies.

All SAEs must be reported to EMD Serono from the time of study drug administration through completion of the study. SAEs that occur after the study-specific informed consent is signed but prior to the first dose of the investigational agent will be collected only if they are considered by the investigator to be causally related to the study required procedures. Probably related SAE will be reported to EMD Serono within 2 business days or 3 calendar days (whichever comes first) of investigator becoming aware.

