10.2.2.4 Immune-Related Adverse Events

Since inhibition of PD-L1 stimulates the immune system, immune-related AEs (irAEs) may occur. Treatment of irAEs is mainly dependent upon severity (NCI-CTCAE grade):

Grade 1 to 2: treat symptomatically or with moderate dose steroids, more frequent monitoring

Grade 1 to 2 (persistent): manage similar to high grade AE (Grade 3 to 4)

Grade 3 to 4: treat with high dose corticosteroids

Table 2 Management of Immune-mediated Adverse Reactions: Guidance in this table is relevant to toxicities probably related to Avelumab. For toxicity attributed to trabectedin, treat according to the protocol or standard of care if treatment is not otherwise specified.

Gastrointestinal irAEs		
Severity of Diarrhea / Colitis (NCI-CTCAE v4)	Management	Follow-up
Grade 1 Diarrhea: < 4 stools/day over Baseline Colitis: asymptomatic	Continue avelumab therapy Symptomatic treatment (e.g. loperamide)	Close monitoring for worsening symptoms Educate subject to report worsening immediately If worsens: Treat as Grade 2, 3 or 4.
Grade 2 Diarrhea: 4 to 6 stools per day over Baseline; IV fluids indicated < 24 hours; not interfering with ADL Colitis: abdominal pain; blood in stool	Withhold avelumab therapy Symptomatic treatment	If improves to Grade ≤ 1: Resume avelumab therapy If persists > 5-7 days or recurs: Treat as Grade 3 or 4.
Grade 3 to 4 Diarrhea (Grade 3): ≥ 7 stools per day over Baseline; incontinence; IV fluids ≥ 24 h; interfering with ADL Colitis (Grade 3): severe abdominal pain, medical intervention indicated, peritoneal signs Grade 4: life-threatening, perforation	Withhold avelumab for Grade 3. Permanently discontinue avelumab for Grade 4 or recurrent Grade 3. 1.0 to 2.0 mg/kg/day prednisone IV or equivalent Add prophylactic antibiotics for opportunistic infections. Consider lower endoscopy.	If improves: Continue steroids until Grade ≤ 1, then taper over at least 1 month; resume avelumab therapy following steroids taper (for initial Grade 3). If worsens, persists > 3 to 5 days, or recurs after improvement: Add infliximab 5mg/kg (if no contraindication). Note: infliximab should not be used in cases of perforation or sepsis.

Dermatological irAEs		
Grade of Rash (NCI-CTCAE v4)	Management	Follow-up

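### Section 9.6 lets the same adverse event be both Probable and Possible, and then counts one as related and the other as unrelated

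*Combined protocol and SAP*

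**What the plan says.** Section 9.6 sets five attribution levels.

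- **Probable** needs a reasonable temporal sequence and an event that "has been previously been described in association with the investigational agent OR cannot reasonably be attributed to other factors".
- **Possible** needs a reasonable temporal sequence, "but could be attributable to other factors such as the subject's clinical state, other therapeutic interventions or concomitant medications". It does not mention whether the event has been described before.
- The closing sentence makes the binary split: "an AE is considered related if it is assessed as definitely or probably related; unrelated if it is assessed as possibly, unlikely related or unrelated".

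The section gives no order of precedence among the levels.

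Four other rules use a probable-relation threshold: the Phase 2 hold in 4.1.2, the DLT definition in 16.2, the last paragraph of 9.8.3 ("Probably related SAE will be reported to EMD Serono within 2 business days") and the header of the immune-related table in 10.2.2.4 ("Guidance in this table is relevant to toxicities probably related to Avelumab"). The DLT definition in 4.1.2 instead takes events rated possible or stronger, and refers to protocol therapy as a whole.

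**The concern.** The two halves of the Probable definition are joined by an OR. The first half can be met when another cause is plausible, and a plausible other cause is what defines Possible. The shared region lies on the line that separates related from unrelated, so the choice of label decides the classification.

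This is not a rare situation in a two-drug regimen for advanced cancer. Fatigue and nausea are reported for avelumab in section 2.5 and are expected toxicities of trabectedin in section 10.3. Disease and concomitant medication can also explain fatigue. If the trial reports treatment-related events with the 9.6 cut, the result depends on rater habit as well as on the data.

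**Working it through.** The plan states no figure on this point, so the check is one of logic.

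**Inputs (all from 9.6).** Let T = reasonable temporal sequence, D = previously described with the agent, C = could be attributed to another factor.

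- Probable, reading A: T and (D or not C).
- Probable, reading B: (T and D) or not C. The sentence does not group its AND and OR, so both readings were tried.
- Possible: T and C.

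**Enumeration.** There are 2 × 2 × 2 = 8 combinations. The four timely ones are:

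| D | C | Probable (A) | Probable (B) | Possible | Result from these two levels |
|---|---|---|---|---|---|
| yes | yes | yes | yes | yes | related and unrelated |
| yes | no | yes | yes | no | related |
| no | yes | no | no | yes | unrelated |
| no | no | yes | yes | no | related |

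In the four untimely combinations Possible always fails, so there is no overlap. Exactly 1 of the 8 combinations meets both definitions, and it does so under either reading: timely, described before, otherwise explainable.

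**Which events fall there.** This depends on what counts as another factor. Section 9.7 records events "from the time of first exposure to the investigational product avelumab", and 10.3 calls trabectedin standard of care. If attribution is to avelumab alone, trabectedin is another factor and toxicities of both drugs fall in the overlap. From 2.5, avelumab-related fatigue was 212/1300 = 16.3% and nausea 108/1300 = 8.3%; both figures reproduce. If attribution is to the regimen, trabectedin drops out as another factor, but the overlap remains for described events that disease or concomitant medication could explain.

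**Effect on a rate.** Let r be the proportion of subjects related on unambiguous events, and q the further proportion whose status rests only on overlap events. The reported related rate can then lie anywhere from r to r + q. One subject is 1/22 = 4.5 percentage points at the minimum enrolment and 1/34 = 2.9 points at the maximum. The documents give no value for q.

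**Which rules the label reaches.**

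- All-causality CTCAE tables: not affected.
- DLTs under 4.1.2: not affected, since Probable and Possible both qualify.
- SAEs to the manufacturer: not affected. Section 9.8.1 sends all SAEs within 2 business days or 3 calendar days, and 9.8.3 repeats that all must be reported.
- IND reports: not affected. Section 9.8.3 applies its own reasonable-possibility standard.
- DLTs under 16.2 and the Phase 2 hold: affected only if the event is also unexpected. Section 9.3 makes that hard to combine with a previously described event, except where severity or frequency is unusual.
- The immune-related table in 10.2.2.4: affected, because its scope is set by the probable label.
- Any related-event summary: affected directly.

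**The case against.** The strongest reply is that little in the plan depends on this label. That is largely right. Safety is a primary endpoint, and a reader might infer that the endpoint itself is unstable. The documents do not support this: 3.1.2 and 3.1.4 define safety by CTCAE grading and an adverse event profile, section 16 plans no related-event rate, and 9.6 offers its cut for general assessment only.

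A reader might also infer a swing of about 50 percentage points, because 2.6 reports that roughly half of the subjects in one trabectedin trial developed Grade 3/4 AST and ALT levels. That does not hold either. The figure comes from 54 subjects on trabectedin alone. Section 9.1 keeps many laboratory abnormalities from being recorded as adverse events at all. The swing would also need every such event to lie in the overlap and be relabelled together, whereas the note after the irAE tables in 10.2.2.4 steers raters towards trabectedin as the likelier cause of hepatic toxicity.

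It is likewise tempting to say that five of the nine toxicities in 10.3 are shared. Only fatigue and nausea have reported avelumab frequencies in this document. The hepatic and renal items appear for avelumab only in management guidance.

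Finally, it is not settled that trabectedin is another factor. Section 9.6 speaks of a study agent and once of agents in the plural form, 7.4 treats both as study drugs, and 9.8.3 judges expectedness for both. This narrows the overlap without closing it.

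What remains is a stated rule that gives two answers for one event.

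**Conclusion.** The point holds in a limited form. The definitions overlap in exactly one combination of criteria, under either reading of the sentence, and that combination is classified as both related and unrelated. Any related-event summary that uses the 9.6 cut is therefore not reproducible. This rests on the wording alone and needs no assumption about event rates.

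No reliable magnitude can be given, because it would require the unknown q. Beyond summaries, the label sets the scope of the immune-related table, and it touches the 16.2 DLT definition and the Phase 2 hold only for events that are also unexpected. This is a correction that should be made, but it does not threaten the response endpoint or expedited reporting.

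**What to change.** For adverse event summaries, change three things in 9.6:

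1. Amend the closing sentence so that related means Definite, Probable or Possible, in line with the attribution threshold of the 4.1.2 DLT definition. The overlapping combination then counts as related under either label.
2. State whether attribution is to avelumab or to the regimen.
3. Add a sentence separating Possible from Unlikely. Both mention other factors. That is harmless while both count as unrelated, but this becomes the new boundary.

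Where the probable label serves other purposes (the Phase 2 hold in 4.1.2, 9.8.3, the table in 10.2.2.4, and 16.2), the sponsor should add a tie-break for events that meet both definitions and reconcile those places with 9.6 and with the 4.1.2 DLT definition, which 16.2 contradicts.

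Deleting the previously-described limb from Probable looks simpler, but it would narrow the set of events that the 10.2.2.4 table covers. That is a clinical-management consequence, and which rule applies there is for the sponsor to decide.

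The cost is a short amendment and re-tabulation of events already recorded. Related-event rates will be somewhat higher than under the present cut.
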